7.2 Toxicity Assessment

Dose reduction should be limited to management of toxicity related to study treatment and not for management of side effects determined by the investigator to be related to underlying disease or other medical condition or concomitant treatment.

If a patient experiences more than one toxicity:

- Dose reduction should be according to the instructions for the toxicity with the higher(est) grade.
- In the case of 2 or more toxicities of the same grade, the investigator may dose reduce according to the toxicity determined to be the most likely to be related to study treatment.

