7.4 General Instructions and Guidelines

- If treatment delays are required, the cycle may be extended to 5 weeks; however, all AR-42 doses must be taken during the first 4 weeks of the 5-week cycle. Any doses not given within the first 4 weeks of the extended cycle will be omitted.
- If one or both of the study medications are held due to toxicity, a **maximum of 3 consecutive weeks is permitted for recovery**. If recovery has not been sufficient to resume treatment 3 consecutive weeks after the decision to hold either or both of the study medications, both study medications must be discontinued.
- If AR-42 treatment must be interrupted for an AR-42-related toxicity, the patient should continue taking pazopanib unless dose modification instructions specifically indicate that pazopanib should be held or omitted.
- If pazopanib treatment must be interrupted due to a pazopanib-related toxicity, the patient should continue taking AR-42 unless dose modification instructions specifically indicate that AR-42 should be held or omitted..

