7.7 Pazopanib Dose Modification Instructions

In addition to the general dose modification instructions provided in Section 7.4, dose modification instructions for pazopanib-related toxicities are listed in Table 7, Table 8 (liver function abnormalities), Table 9 (PPE), and Table 10 (Other).

Note: For some toxicities, AR-42 instructions are also included on the tables listed above.

Toxicity	Pazopanib Modification			
	(Refer to Table 6 for pazopanib dose reduction steps)			
Cardiac	Hold/omit ^A pazopanib and determine LVEF.			
Grade 2 heart failure	 If < 15% absolute decline in LVEF compared with baseline or a decline in LVEF of < 10% compared with baseline and ≥ 50%: When symptoms of heart failure show clinical improvement, resume pazopanib with reduction in dose of one dose reduction step.^B If ≥ 15% absolute decline in LVEF compared with baseline or a decline in LVEF of ≥ 10% compared with baseline and < 50%: Continue holding until clinical improvement in symptoms and until LVEF improves to within 10% of baseline. Refer patient for cardiology consult. Reduce pazopanib dose by one dose reduction step when resuming treatment.^B At investigator's discretion, pazopanib may be discontinued. 			
Grade 3 or 4 heart failure	Discontinue pazopanib (also discontinue AR-42).			
Grade 3 or 4 MI	Discontinue pazopanib (also discontinue AR-42).			
Endocrine Disorders				
Grade 2 hypothyroidism	Continue pazopanib (dose reduction not required); initiate hypothyroidism management.			
Grade 3 or 4 hypothyroidism	Discontinue pazopanib; initiate/continue hypothyroidism management.			
Gastrointestinal Disorders				
≥ Grade 1 fistula	Discontinue pazopanib (also discontinue AR-42).			
≥ Grade 2 perforation				
Investigations				

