7.7.2 PPE

Refer to Section 6.9.4 for supportive care instructions and recommendations for the prevention and treatment of PPE. Refer to the table below for study treatment instructions.

Grade of event (NCI CTCAE v4.0)	Occurrence	Pazopanib Dose Modification ^A (Refer to Table 6 for pazopanib dose reduction steps.)
 Grade 1 Minimal skin changes or dermatitis (eg, erythema, edema, hyperkeratosis) without pain Numbness, dysesthesia, paresthesia, tingling, painless swelling, or erythema of hands and/or feet Does not disrupt normal activities 	Any	Continue study treatment; maintain dose level.
 Grade 2 Skin changes (eg, peeling, blisters, bleeding, edema, or hyperkeratosis) with pain Painful erythema and swelling of hands and/or feet Limiting instrumental ADL^B 	Any	 If PPE is NOT interfering with instrumental ADL, maintain pazopanib (and AR-42) dose. If PPE is interfering with instrumental ADL, reduce pazopanib by one dose reduction step for the remainder of the treatment cycle.^C If no improvement in spite of supportive care and pazopanib dose reduction, omit pazopanib for the remainder of the cycle. When resuming treatment, decrease pazopanib dose by one dose reduction step.^{C,D}
Grade 3 • Severe skin changes (eg, peeling, blisters, bleeding, edema, or	1 st Occurrence	 Omit pazopanib and AR-42 for a minimum of 7 days and until toxicity resolves to ≤ grade 1.^D When resuming treatment, decrease pazopanib dose by one dose reduction step.^C
 hyperkeratosis) with pain Moist desquamation, ulceration, blistering, or severe pain of the hands and/or feet 	2 nd Occurrence	 Omit pazopanib and AR-42 for a minimum of 7 days and until toxicity resolves to ≤ grade 1.^D When resuming treatment, decrease pazopanib dose by one dose reduction step.^C
Limiting self-care ADL ^E	3 rd Occurrence	Discontinue pazopanib and AR-42.

Table 9	Pazonanih	Dose	Modification	Instructions for	r PPF
Table 5.		0030	mounication	monuono ic	

A. More conservative management is permitted per investigator discretion.

B. Instrumental ADL refer to preparing meals, shopping for groceries or clothes, using the telephone managing money, etc.

C. If toxicity returns to ≤ grade 1 after dose reduction, pazopanib escalation is permitted, **up to the enrolled dose level**, at the discretion of the investigator if the patient has completed 1 cycle at a reduced dose without recurrence of the event.

D. If > 3 consecutive weeks of delay are required for recovery, discontinue pazopanib and AR-42.

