- H. If urinalysis reading for protein is ≥ 2+ (100 mg/dL), a 24-hour urine sample must be collected and tested (see Section 4.1.6 for related eligibility criterion).
- I. Refer to Section 4.2.13, Section 6.8, and Table 7 for instructions related to QTc interval prolongation.
- J. Assessment may be performed by echocardiogram or by a nuclear study (eg, MUGA scan; first-pass technique).
- K. Determination of LVEF is required within 3 months prior to cycle 1, day 1 study treatment.
- L. Baseline imaging **must be contrast-enhanced** and include the following:
 - Chest CT, CT or MRI of abdomen and pelvis, and all other suspected sites of disease **within 28 days** prior to initiation of study treatment; for patients with a CT contrast allergy, the chest CT may be performed without contrast or, if the chest is not a known site of disease, a chest x-ray may be used
 - Brain CT or MRI within 8 weeks prior to initiation of study treatment
- M. Collection of tumor samples archived following the most recent biopsy or surgery; tumor samples must be requested by the end of cycle 2 (Section 11).
- N. Refer to Sections 6.1 through 6.6 for treatment-related instructions including the AR-42 and pazopanib dose levels.
- O. If cycle has been extended to 5 weeks, AR-42 doses must be given during the 1st 4 weeks of the cycle allowing a 1-week AR-42 rest period (Section 6.2.1); pazopanib continues daily.

Tests, Exams, and Other Requirements	Cycle 2		Cycle 3	Cycle 4	End of	End of
	Day 1 ^A	Day 15 ^B	Day 1 ^A	Day 1 ^A	Treatment ^c	30-Day Follow-Up
Weight	Х		Х	Х	Х	
Vital Signs	Х		Х	Х	Х	
BP	Х	Х	Х	Х	Х	
Performance Status	Х		Х	Х	Х	
Assessment of AEs	Х		Х	Х	Х	XD
Concurrent Medications ^E	Х		Х	Х	Х	
Physical Exam	Х		Х	Х	Х	
CBC with Differential	Х	Х	Х	Х	Х	
Platelet Count	Х	Х	Х	Х	Х	
Serum Chemistry ^F	XF	XF	XF	X ^F	Х	
Lipase	Х		Х	Х	Х	
TSH and T4				X ^G (Every 3 cycles)		
Urinalysis for Protein			Х ^н (Every 2 cycles)			
12-Lead ECG ^I	х			X ^J (Every 2 cycles)		
LVEF Assessment ^K				X ^L (Every 3 cycles)		
Tumor Imaging/Disease Assessment ^M			X ^N (Every 2 cycles)		x	0
Correlative Tumor Sample Collection	х	P				
AR-42 PO ^Q	Once	daily 3 days/w				
Pazopanib PO ^Q	Once daily continuously ^R					
Study Medication Diary Review & Pill Count	Х		Х	Х	х	

72

 Table 20. Study Calendar – Treatment Beginning with Cycle 2 Through Follow-Up

Table 20 Footnotes:

- A. Within 3 days prior to or on day 1 of each treatment cycle.

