- B. Within 3 days prior to or on day 15.
- C. Within 2 weeks after the end of study treatment.
- D. If the patient is unable to return for a study visit at this time, the study team may contact the patient, family member, and/or other care providers to get information needed to complete the AE assessment at this time point.
- E. Include over-the-counter medications.
- F. Serum chemistry includes the following panels and tests: basic metabolic panel (sodium, potassium, carbonate, chloride, glucose, calcium, BUN, and creatinine); hepatic panel (ALT, AST, ALP, total bilirubin, direct bilirubin, albumin, and total protein); and magnesium and phosphorous. (Refer to Table 8 for instructions regarding increased frequency of liver function monitoring **[weekly for at least 4 weeks]** when pazopanib-related elevations [AST, ALT, bilirubin] occur.)
- G. Following completion of 3 cycles of study treatment beginning on day 1 of cycle 4, repeating on day 1 of cycle 7, and continuing after every 3 cycles of treatment (ie, about every 3 months).
- H. Following completion of 2 cycles of study treatment beginning on day 1 of cycle 3, repeating on day 1 of cycle 5, and continuing after every 2 cycles of treatment (ie, about every 2 months). *If urine protein is* 2+ (100 mg/dL), a 24-hour urine sample must be collected and tested.
- I. Refer to Section 6.8 and Table 7 for instructions related to QTc interval prolongation.
- J. On day 1 (+/- 1 week) of cycles 4, 6, and continuing after every 2 cycles of treatment (ie, about every 2 months [+/- 1 week]).
- K. LVEF assessment should be performed using the same method used at baseline to determine eligibility.
- L. Following completion of 3 cycles of study treatment beginning on day 1 of cycle 4 (+/- 1 week), repeating on day 1 of cycle 7 (+/- 1 week), and continuing after every 3 cycles of treatment (ie, about every 3 months [+/- 1 week]).
- M. Imaging may be limited to known sites of disease. Brain imaging required for patients with brain metastasis diagnosed and treated prior to initiation of study treatment. The imaging used at baseline should be used at each subsequent imaging time point.
- N. Following completion of 2 cycles of study treatment beginning on day 1 of cycle 3 (+/- 1 week) and continuing after every 2 cycles of treatment (ie, about every 2 months [+/- 1 week]); see Section 10.

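### Table 7, grade 2 heart failure: a fall of 10 to under 15 points to an LVEF below 50% meets both LVEF branches, and their restart instructions conflict

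*Combined protocol and SAP*

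**What the plan says.** For grade 2 heart failure, Table 7 in section 7.7 first holds pazopanib and has LVEF measured. It then gives two branches.

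- **First branch:** "If < 15% absolute decline in LVEF compared with baseline or a decline in LVEF of < 10% compared with baseline and ≥ 50" per cent. Pazopanib resumes one dose step lower when symptoms improve.
- **Second branch:** "If ≥ 15% absolute decline in LVEF compared with baseline or a decline in LVEF of ≥ 10% compared with baseline and < 50" per cent. The instruction is "Continue holding until clinical improvement in symptoms and until LVEF improves to within 10% of baseline", with referral to cardiology and a restart one step lower.

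Only the 15% threshold is labelled absolute. The 10% in each branch, and in the recovery criterion, has no label.

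Section 7.4 caps any toxicity hold: if recovery is insufficient "3 consecutive weeks after the decision to hold either or both of the study medications, both study medications must be discontinued".

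**The concern.** The two branches look like opposites but are not. The inequalities were reversed between them, while *or* and *and* stayed where they were. The exact opposite of *A or (B and C)* is *not A and (not B or not C)*, so both the inequalities and the connectives have to change.

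The result is a band of patients who satisfy both conditions. Both branches hold the drug, wait for symptom improvement and resume one step lower. The second adds two requirements: documented LVEF recovery and a cardiology consult. A patient in the band is therefore under two instructions that disagree on when pazopanib may restart. What is at stake is the cardiac safety of that patient.

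**Working it through.** **Inputs.** The two conditions come from Table 7. Entry requires a baseline LVEF of at least 50% (section 4.1.11). Let b be baseline LVEF, l the on-treatment value and d = b − l, all in percentage points.

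**Printed conditions, with *and* binding before *or* and 10% read as points:**
- First: d < 15, or (d < 10 and l ≥ 50).
- Second: d ≥ 15, or (d ≥ 10 and l < 50).

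**Worked case.** b = 60, l = 48, d = 12. First: 12 < 15, met. Second: 12 ≥ 10 and 48 < 50, met. The second branch then requires recovery to 60 − 10 = 50 if 10% is absolute (2 more points), or 0.9 × 60 = 54 if relative (6 more points). The first requires neither.

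**Extent of the overlap.** Take whole-number baselines 50 to 75 and on-treatment values from 10 up to baseline, 1,391 pairs.
- Absolute 10%: the overlap is d = 10 to 14 with l < 50. Baselines 50 to 59 give 5 values each (50 pairs); baselines 60, 61, 62 and 63 give 4, 3, 2 and 1 (10 pairs). Total 60.
- Relative 10%: the total rises to 91 and contains all of the 60.
- No pair falls in neither branch under either reading.

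These counts show where the overlap lies. They are cells of an arbitrary grid, not probabilities.

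**Which branch was meant.** The first branch's later clause adds no pair, since a decline under 10% on either reading is already under 15 points on this grid. Every pair that the second branch's later clause adds (60 or 91) also meets the first branch. If the first branch governed, that clause would do nothing, so the second was evidently meant to govern.

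**Alternative grouping.** Let the 50% qualifier apply to both halves of each branch, with 10% absolute:
- First: d < 15 and l ≥ 50.
- Second: d ≥ 10 and l < 50.

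The overlap disappears and 60% to 48% falls only in the second. But 70% to 52% (d = 18, l = 52) now meets neither, and nor does 52% to 48% (d = 4, l = 48). On the same grid, 111 pairs meet neither (80 if 10% is relative). This grouping does not repair the table.

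**Search for a precedence rule.**
- Section 7.2: "Dose reduction should be according to the instructions for the toxicity with the higher(est) grade". This is for a patient with more than one toxicity; here there is one toxicity at one grade.
- Section 7.4 and the Table 7 footnotes set no order between the branches.
- "More conservative management is permitted per investigator discretion" is a footnote to Table 9 (PPE), not to Table 7.

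**How many patients.** The only related rate in the public text is Table 17: left ventricular dysfunction of any grade in STS, 8% on pazopanib against 4% on placebo. If all 29 to 35 expected patients had STS, that gives 0.08 × 29 = 2.3 to 0.08 × 35 = 2.8 patients. RCC patients also enrol, and the RCC tables do not list the event. Grade 2 heart failure with an LVEF in the band would be an unstated fraction of these.

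**The case against.** The strongest reply is that a sensible investigator would apply the second branch. It gives effect to every clause, it is the more cautious, and the LVEF below 50% is known before a branch is chosen. That stands as a reading of intent. It does not replace a rule: the first branch's condition is also met, and nothing ranks the two.

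A second reply is that the row has no brackets and the table was read as extracted text, so grouping shown by layout cannot be checked. The one alternative grouping tested leaves gaps, so the row needs rewording under either.

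Two stronger inferences are tempting, and the documents support neither.

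- A reader might infer that restarting under the first branch would not be a deviation. The patient has also triggered the second branch, whose instruction to keep holding would go unfollowed. The documents do not settle whether that is a deviation.
- A reader might infer that the overlap opens a gap of about 12 weeks (3 cycles of 4 weeks) in LVEF monitoring. Routine LVEF is every third cycle, "beginning on day 1 of cycle 4 (+/- 1 week), repeating on day 1 of cycle 7 (+/- 1 week", after a restart under either branch. The difference lies before restart: the recovery criterion and the consult.

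Other safeguards also remain. Physical exam and AE assessment are scheduled "Within 3 days prior to or on day 1 of each treatment cycle". Recurrent grade 2 heart failure triggers a new hold and LVEF. Sections 5.2 and 6.5 let the investigator stop treatment in the patient's interest, and section 14.1 requires study team review at least monthly.

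**Conclusion.** The concern holds as a minor drafting error in a safety rule. Read with *and* before *or*, Table 7 gives conflicting restart instructions for grade 2 heart failure with a fall of 10 to under 15 points to an LVEF below 50%. If 10% is relative, the band is wider. The second branch is evidently the intended one, but the protocol does not say so.

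Few patients, possibly none, would be affected. This is individual safety management: the DLT definition, the sample size and the analysis do not change. The conclusion rests on the grouping stated above; the alternative grouping exchanges the overlap for gaps.

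**What to change.** Keep the second branch as printed and make the first its exact complement: *absolute decline < 15% AND (decline < 10% from baseline OR LVEF ≥ 50%)*. On the same grid this leaves 0 pairs in both branches and 0 in neither, whether 10% is absolute or relative. Alternatively, add a sentence that the second branch prevails whenever its criteria are met.

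Also state one meaning of 10% for both branches and the recovery criterion. The documents do not settle which. The absolute reading is the less protective: a fall from 55% to 48% (7 points; 7/55 = 12.7% relative) would stay in the first branch, whereas the relative reading puts it in the second.

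The change is one line of Table 7, by amendment. Its clinical cost is a repeat LVEF and a cardiology consult for the few patients in the band. Some may reach the 3-week hold limit and stop both drugs. That is more likely if 10% is defined as relative, where up to 9 further points of recovery are needed in the overlap, against up to 4 if absolute.

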4.2 Exclusion Criteria

A patient who meets any of the following exclusion criteria is not eligible to participate in this study.

- 4.2.1 Symptomatic or untreated brain metastasis
- 4.2.2 Leptomeningeal metastasis
- 4.2.3 Any investigational agent within 4 weeks prior to initiating study treatment

- 4.2.4 Previous therapy with pazopanib
- 4.2.5 Inability to swallow medication
- 4.2.6 Known or suspected malabsorption condition or obstruction
- 4.2.7 Contraindication to antiangiogenic agents, including:
 - Serious non-healing wound, non-healing ulcer, or bone fracture
 - Major surgical procedure or significant traumatic injury within 4 weeks prior to initiating study treatment; other surgical procedures within 2 weeks prior to initiating study treatment
 - Pulmonary hemorrhage/bleeding event ≥ grade 2 within 12 weeks prior to initiating study treatment
 - Any other hemorrhage/bleeding event ≥ grade 3 within 12 weeks prior to initiating study treatment
- 4.2.8 History of organ allograft including corneal transplant
- 4.2.9 Evidence of bleeding diathesis or coagulopathy
- 4.2.10 Documented Gilbert's Syndrome
- 4.2.11 Resting systolic blood pressure (BP) < 100 mmHg
- 4.2.12 Hypertension defined as systolic BP ≥ 140 mmHg **or** diastolic BP ≥ 90 mmHg despite optimal medical management
- 4.2.13 QTc interval > 450 ms on screening 12-lead electrocardiogram (ECG)
 - If baseline QTc on screening ECG meets exclusion criteria:
 - Check calcium, potassium, and magnesium serum levels.
 - Correct any identified hypocalcemia, hypokalemia, and/or hypomagnesemia and repeat ECG to confirm exclusion of patient due to prolonged QTc interval.
 - For patients with heart rate (HR) 60-100 bpm, manual read of QTc is not required.
 - For patients with a baseline HR < 60 bpm or > 100 bpm, manual read of the QT interval by a cardiologist is required, with Fridericia correction applied to determine QTc (ie, QTcF).
- 4.2.14 Active or clinically significant cardiac disease including any of the following:
 - Unstable angina (eg, anginal symptoms at rest) or onset of angina within 3 months prior to initiating study treatment
 - Myocardial infarction within 6 months prior to initiating study treatment
 - Cardiac arrhythmias currently requiring anti-arrhythmic therapy other than beta blockers

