6.9.5 Hypertension

Hypertension, including hypertensive crisis, has been observed during pazopanib therapy. Hypertension should be managed aggressively to prevent complications. Management of hypertension is at the investigator's discretion.

- BP will be monitored weekly during the first 6 weeks of study treatment, at the beginning of every cycle beginning with cycle 3, and as clinically indicated throughout study treatment.
- Refer to Table 7 for grading definitions to be used for pazopanib dose modifications related to hypertension and for treatment instructions. CTCAE v4.0 will be used to grade hypertension for AE reporting purposes.

Note: Grade 3 hypertension will not be considered a DLT unless the patient is experiencing symptoms of hypertension and/or grade 3 hypertension persisted longer than 7 days. This guideline also applies to hypertension requiring an additional antihypertensive agent(s).

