7.3 Toxicity Grading

AEs will be characterized and graded according to NCI CTCAE v4.0.

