7.6 Pazopanib Dose Reduction Guidelines

Treatment with pazopanib will be interrupted and/or the dose reduced for clinically significant toxicities that are related to pazopanib therapy. Dose modifications will follow predefined dose reduction steps according to the guidelines shown on the table below.

Dose	Reduced Pazopanib Dose				
Reduction Step	When Starting Dose is 600 mg	When Starting Dose is 800 mg			
- 1	400 mg	600 mg			
- 2	200 mg 400 mg				
- 3	Discontinue pazopanib	200 mg			
- 4	Not Applicable Discontinue pazopanib				
*The pazopanib dose indicated on this table should be taken according to the same instructions and schedule outlined in Section 6.2.2 .					

 Table 6. Pazopanib Dose Reduction Steps for Toxicity Management

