	 calcium abnormalities are corrected, symptoms resolved, and QTc improved to ≤ grade 1 (≤ 480ms). Reintroduce pazopanib and AR-42 with input from cardiology and with additional QTc evaluation, either concurrent with reintroduction or at earliest possible opportunity within 8 days from reintroduction. If event is thought to be related to study treatment, reduce the dose of pazopanib and AR-42 by one dose reduction step when resuming study treatment.^B Consider chronic supplementation for maintenance of electrolytes. For recurrent syncope or near-syncope thought to be related to study treatment, consider discontinuation of both pazopanib and AR-42.
Renal and Urinary Disorders	
≥ Grade 2 proteinuria	 Hold/omit^A pazopanib. If assessment of proteinuria was based on a urine dipstick reading, a 24-hour urine collection is required. Based on the 24-hour urine specimen: If grade 2 proteinuria, consult nephrology. If urine protein is < 3.0 gm/24 hours, study treatment may be continued without dose modification pending nephrology consult. If ≥ 3.0 gm/24 hours, hold study treatment until improvement to < 3.0 gm/24 hours or additional nephrology recommendations. If grade 3 proteinuria, consult nephrology and discontinue pazopanib.
Respiratory, Thoracic, and M	ediastinal Disorders
≥ Grade 2 pneumonitis	Discontinue pazopanib (also discontinue AR-42).
Skin and Subcutaneous Disc	rders
PPE (hand-foot syndrome)	See Table 9 for instructions related to PPE

Table 7. Pazopanib Dose Modification Instructions (continued)

Table 7. Pazopanib Dose Modification Instructions (continued)

Tuble III azopanie Beee mea	
Vascular Disorders	
Grade 3 hypertension defined as systolic BP >160 mmHg and diastolic BP >100 mm/Hg	 Hold/omit^A pazopanib until resolution to ≤ grade 2. Administer standard antihypertensive therapy. When resuming pazopanib, decrease pazopanib dose by one dose reduction step; monitor BP weekly for 4 weeks. If BP remains controlled for at least one cycle, the pazopanib dose may be escalated by one dose step at the investigator's discretion.
Grade 4 hypertension	Discontinue pazopanib (also discontinue AR-42)
	an the first 4 weeks of the cycle, any remaining doses for that cycle are 7.4 for additional information.

B. At the investigator's discretion (after the DLT evaluation period [Section 6.7.1]), the dose may be escalated by one dose step when the toxicity has resolved and treatment can be resumed.

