7.7.3 Other Toxicity

The instructions on the table below should be followed for toxicities not addressed on the previous dose modification tables.

Table 10. Pazopanib Dose Modification for Other Toxicity

NCI CTCAE v4.0	Initiation of Treatment Cycle	Dosing Interruption During the Cycle ^A	Dose Modification If Treatment Resumed During the Same Cycle ^A	Dose for Subsequent Cycles ^A		
Grade 1	Start cycle on time	Continue treatment (no interruption)	Not Applicable	No change		
Grade 2	Start cycle on time or delay start of the cycle until ≤ grade 1 or baseline grade per investigator discretion ^B	Continue treatment or interrupt dosing (pazopanib and AR-42) until resolution to \leq grade 1 or baseline grade per investigator discretion ^B	No change or reduce pazopanib dose by one dose reduction step per investigator discretion ^C	No change or reduce pazopanib dose by one dose reduction step per investigator discretion ^C		
Grade 3	Delay start of the cycle until ≤ grade 1 or baseline grade ^B	Interrupt dosing until resolution to ≤ grade 1 or baseline grade ^B	Reduce pazopanib dose by one dose reduction step ^c	Reduce pazopanib dose by one dose reduction step ^c		
Grade 4Delay start of the cycle until \leq grade 1 or baseline grade ^B Omit dosing for the remainder of the treatment cycleReduce pazopanib dose by one dose reduction step or discontinue both pazopanib and AR-42 per investigator's discretion ^C If grade 4 toxicity recurs at reduced pazopanib dose, discontinue both pazopanib and AR-42						
 A. Excludes alopecia, nausea and vomiting that improve with antiemetic therapy, hypersensitivity that improves with medical management, and laboratory abnormalities that are asymptomatic and/or not clinically significant in the opinion of the investigator. B. If treatment cannot resume after a 3 week delay, pazonanib and AP, 42 must be discontinued. 						

B. If treatment cannot resume after a 3-week delay, pazopanib and AR-42 must be discontinued.

C. Refer to Table 6 for pazopanib dose reduction steps.

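### The pazopanib hold for grade 3 hypertension requires both systolic and diastolic limits to be exceeded, so a marked rise in one alone does not trigger it

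*Combined protocol and SAP*

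**What the plan says.** The Vascular Disorders rows of Table 7 (Section 7.7) give the hypertension rules for pazopanib. The trigger for a hold is "Grade 3 hypertension defined as systolic BP >160 mmHg and diastolic BP >100 mm/Hg". Once it is met, pazopanib is held until the event is grade 2 or lower, antihypertensive treatment is given, pazopanib resumes one step lower, and blood pressure is checked weekly for 4 weeks. A separate row stops both drugs for grade 4 hypertension but gives no blood pressure value.

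Section 6.9.5 refers the reader to Table 7 "for grading definitions to be used for pazopanib dose modifications related to hypertension and for treatment instructions" and keeps CTCAE v4.0 for adverse event reporting. Section 7.3 gives the general default: "AEs will be characterized and graded according to NCI CTCAE v4.0".

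Other provisions bear on a raised blood pressure. Section 6.9.5 states "Hypertension should be managed aggressively to prevent complications" and leaves management to the investigator. Section 7.6 states "Treatment with pazopanib will be interrupted and/or the dose reduced for clinically significant toxicities that are related to pazopanib therapy". Section 7.7.3 introduces Table 10 with "The instructions on the table below should be followed for toxicities not addressed on the previous dose modification tables".

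At entry, criterion 4.2.12 excludes "Hypertension defined as systolic BP ≥ 140 mmHg or diastolic BP ≥ 90 mmHg despite optimal medical management".

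**The concern.** Read literally, the Table 7 trigger fires only when both components exceed their limits. A patient with severe systolic hypertension and a diastolic of 100 mmHg or less, or the reverse, falls outside it.

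This is the protocol's only hypertension hold rule with a blood pressure threshold. If it does not fire, holding or reducing pazopanib depends on individual judgement instead of a stated limit. The weekly checks tied to restart are not required either, and from cycle 3 the scheduled measurement is only at the start of each cycle, plus any that are clinically needed.

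The wording also affects restart. If grade 3 needs both components, a held patient can be read as back to grade 2 or lower as soon as one of them falls to its limit.

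At stake are patient safety and consistent dose modification. The frequency of dose modifications is one of the inputs to the RP2D judgement in Section 6.7.4, so uneven application also makes that input less reliable.

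**Working it through.** The plan gives no calculated figure to reproduce here. The check is of the logic of the rule, followed by simple arithmetic for scale and cost.

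**1. Trigger.** The limits are systolic >160 and diastolic >100 mmHg (Table 7). The readings are illustrations.

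| Reading (mmHg) | Systolic >160 | Diastolic >100 | 'and' (as written) | 'or' |
|---|---|---|---|---|
| 195/98 | yes | no | no hold | hold |
| 150/115 | no | yes | no hold | hold |
| 170/105 | yes | yes | hold | hold |
| 158/98 | no | no | no hold | no hold |

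The two versions differ exactly when one component is above its limit and the other is not.

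**2. Restart.** Take a patient held at 175/105. At 175/99 the diastolic condition fails, so the reading is no longer grade 3 under Table 7. The requirement of grade 2 or lower can then be read as met while systolic is still above 160. Section 7.3 offers CTCAE v4.0 as the general grading, but Table 7 sets its own grade 3 numbers and gives none for grade 2.

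**3. Does other text close the gap?**
- *Section 6.9.5:* asks for aggressive management but sets no limit and leaves it to the investigator.
- *Section 7.6:* depends on what is judged clinically significant.
- *Table 10:* covers toxicities not addressed in the earlier tables. Hypertension has Table 7 rows, and the text does not say whether a lesser elevation counts as unaddressed. If Table 10 applied by CTCAE v4.0 grade, its grade 3 row would require "Interrupt dosing until resolution to ≤ grade 1 or baseline" and a reduction, while its grade 2 row lets treatment continue.
- *Table 7, grade 4 row:* gives no blood pressure value.
- *Section 9.2.10:* points to the prescribing information, which is not among the documents.

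None of these sets a compulsory hold at a stated reading.

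**4. Internal comparison.** Criterion 4.2.12 joins the same two components with an emphasised 'or'. Elsewhere the connectors carry meaning: the LVEF entry in Table 7 uses 'or' and 'and' for different conditions, and Table 8 uses 'and' where raised transaminases and raised bilirubin must coincide. A site would therefore take the 'and' in the hypertension row at face value.

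**5. Scale.** Grade 3 hypertension on pazopanib alone was 4% in RCC (Table 13) and 7% in STS (Table 16), with grade 4 at 0% in both. The likely sample size is 29 to 35 (Section 13.2). Expected patients = rate × n:
- 0.04 × 29 = 1.16 and 0.07 × 29 = 2.03
- 0.04 × 35 = 1.40 and 0.07 × 35 = 2.45

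That is about 1.2 to 2.5 patients with any grade 3 hypertension, not the subset with one component raised.

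**6. Room for a hold in cycle 1.** Section 6.7.1 requires at least 21 pazopanib doses for DLT evaluability.
- 28-day cycle: 28 − 21 = 7 doses can be missed. An 8-dose hold leaves 28 − 8 = 20, below the minimum.
- Cycle extended to 5 weeks, with recovery within the first 4: 35 − 21 = 14 doses can be missed.

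**The case against.** The strongest reply is that 'and' may be deliberate. Section 6.9.5 gives dose modification its own grading, separate from CTCAE v4.0, and leaves management to the investigator. The DLT definition exempts asymptomatic grade 3 hypertension lasting up to 7 days. A narrow compulsory hold would fit a plan to treat the blood pressure first and cut the drug second. Criterion 4.2.12 has different limits and a different purpose, so its 'or' does not settle intent.

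Blood pressure is also checked weekly for the first 6 weeks in any case, and investigators can interrupt or stop treatment on their own judgement. The number affected is unknown and could be below one. Under 'or', a sustained asymptomatic 162/80 would force a hold and a reduction even if antihypertensives would control it. More reductions would feed into the RP2D judgement.

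Much of this stands. Intent is unproven, the number is unknown, little monitoring is lost in the first 6 weeks, and the effect on dose modification counts is real though small. It does not rescue the rule. The remaining cover is discretionary or carries no number, and the plan already regards these limits as serious enough for a compulsory hold when both are exceeded. Nothing in the text explains why 195/98 should be exempt.

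**Conclusion.** The concern holds. As written, the only hypertension hold with a blood pressure threshold does not fire for a marked rise in one component, and the restart condition can be read as met while the other component is still above its limit. What is lost is mandatory action; discretionary action remains available.

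The number of patients affected cannot be derived. The 1.2 to 2.5 figure is only an indication of how often grade 3 hypertension of any pattern might occur. It assumes that the pazopanib-alone rates carry over. Those were graded under CTCAE v3.0, whose limits the documents do not give, and they exclude any added effect of AR-42. The case rests on a safety rule that fails on its face, not on frequency. The DLT definition, the MTD rule and the sample size do not change. Confidence in the reading of the text is high. That 'and' was a slip is an inference.

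**What to change.** In the Table 7 grade 3 hypertension row:
- Change the trigger to: systolic BP >160 mmHg or diastolic BP >100 mmHg, confirmed on a repeat reading.
- State the restart condition as: until systolic BP is ≤160 mmHg and diastolic BP is ≤100 mmHg.

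The sponsor's clinicians should confirm the thresholds and the repeat interval, so that a single transient reading such as 161/80 does not force a hold. If 'and' is intended, the protocol should say so and give the reason.

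The cost is two wording changes in one row, a repeat reading when a limit is crossed, and a few more holds and one-step reductions, which will appear in the dose modification counts used for the RP2D. In cycle 1, a hold beyond the dose margin shown above would make a patient without a DLT inevaluable, and Section 13.6.1 would then require replacement. Section 13.2 already allows for up to 20% inevaluable patients. Rechecking blood pressure during a cycle 1 hold, before the next weekly visit, would limit such losses.
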